5 PROCEDURES

5.1 Study procedures. Using lay language, provide a complete description of the study procedures, including the sequence, intervention or manipulation (if any), time required, and setting/location. If it is available and you think it would be helpful to the IRB: Upload a study flow sheet or table to the **Supporting Documents** SmartForm in **Zipline**.

For studies comparing standards of care: It is important to accurately identify the research procedures. See UW IRB [POLICY: Risks of Harm from Standard Care](#) and the draft guidance from the federal Office of Human Research Protections, ["Guidance on Disclosing Reasonably Foreseeable Risks in Research Evaluating Standards of Care"](#); October 20, 2014.

Overview: This is a 3-arm randomized clinical trial of 600 individuals with LTPD. Self-report survey assessments will be conducted at baseline, 3 months, 7 months, and 12 months. Study participants will be randomly assigned to one of three conditions, each lasting 6 months: (1) The intervention (EW-D), (2) a wellness education control, or (3) treatment as usual (TAU). A subset of participants will provide GPS/diary data about their community activities. See Figure 1 for study flow.

Individuals who are both eligible and interested in participating in this study will complete informed consent using: a) Electronic signature via a DocuSign account set-up by the University of Washington OR b) By mailing the consent form, a cover letter, and a return envelope to the participant. The procedures associated with the study group will start once we receive the individual's signed electronic or paper consent and once they have completed the baseline survey.

Study Arm Randomization: After completing the baseline survey, individuals will be randomized into one of the three study arms. Participants will be randomized using a randomization script (Appendix 23).

Before initiating the intervention study, up to 10 pilot participants will provide feedback on the recruitment and enrollment process and materials, the baseline survey, and the GPS/travel diary procedures and materials (procedures described in more detail below).

[figure not shown]
Description and procedure for each study arm:

GROUP 1: Adapted EnhanceWellness-Disability (EW-D) Intervention

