What is the EnhanceWellness-Disability (EW-D) intervention? EW-D is a collaborative, patient-centered program designed to work across disease types. It is used in King County by Sound Generations (formerly Senior Services) to target older adults. In EW-D, participants work one-on-one with the study Wellness Coach (the coach will be UW study staff typically a master's level social worker or registered nurse who will be trained by Sound Generations, the legal owner of the EnhanceWellness intervention). The participant and wellness coach will work together to identify health self-management problems, consider options, develop goals and an action plan, and make adjustments to that plan over time. Goals are participant selected. They may include any aspect of wellness, participation, or health the participant wishes to address, including (but not limited to) health behavior change, changes in physical activity, specific disease or symptom self-management, reduction in health risk factors, plans to increase meaningful socialization, addressing workplace accommodations, parenting stressors, retirement planning, new declines in physical function, involuntary retirement, and emergence of new chronic medical comorbidities. The Wellness Coach works with the participant through a combination of motivational interviewing, problem solving, and referral to community resources as needed. The program is designed to last 6 months.

Procedures: Prior to starting their EW-D sessions, participants will complete the baseline study survey for the first time (completion time is about 45 minutes; **Appendix 8**) as well as the baseline GPS week (if randomized to the GPS). As part of the EW-D intervention, participants in this group only will respond to another set of questions that are a feedback tool designed to help the Wellness Coach tailor the intervention sessions (completion time is about 20 minutes; **Appendix 9**). Then, we will connect the participant with their Wellness Coach to schedule their first session (all sessions will be conducted over the telephone or Zoom HIPAA compliant video call and each session is expected to last about 1 hour). The first session or two will consist of an overview of the program, review of these EW-D questionnaire responses, and determining their health or behavior related goal with the

Figure 1. Participant Flow Diagram (Version 3)

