GROUP 3: Treatment as Usual (TAU) To establish a baseline comparison for treatment effects, participants in the TAU arm will not receive contact with a study social worker, will not receive education or fact sheet information, and will be asked to continue with their lives as they normally would. Similar to groups 1 and 2, TAU participants will complete the self-report surveys as described below.

Additional study information:

Outcome Data (GPS/diary): To objectively measure community activity and participation behavior, we will collect a combination of Global Position System (GPS) data, in conjunction with daily self-report travel diaries from a sub-set of participants (**Appendix 27, 38**).

Of the 600 individuals enrolled in the study, a subset of participants (N=100 per arm; 300 total) will be invited to a one week GPS/diary study component at two time points (at baseline and again at the 12-month assessment). Participants will be mailed a cover instruction letter, along with the portable GPS data logger (such as, QStartz BT Q1000XT GPS logger), 1 weeks' worth of paper daily travel diaries (**Appendix 27**), and an additional GPS letter with notes for completing the week of GPS data logging (**Appendix 30**). Participants will also be given the option of completing the Travel Log electronically. Participants who wish to complete the travel log electronically will be emailed an excel version of the travel log (**Appendix 38**) in addition to the paper version.

- The GPS device is small (72 x 47 x 20mm; 64.g) and can be attached with Velcro to a belt or wheelchair, or can be placed in a pocket, purse, backpack, etc. This portable device works up to 24 hours on a single charge when set at a 15 sec epoch acquisition. Participants will be provided with a charger and instructed to charge the device nightly, power them on in the morning, wear them during waking hours, and remove them at bed time. Participants will be told to go about their daily routine as they normally would.

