Per sponsor request, we will have a Certificate of Confidentiality (CoC) in place prior to beginning GPS/diary data collection.

Outcome Data (Self-report Surveys): All 3 groups will complete a baseline (prior to intervention), 3-month (mid-intervention), 7-month (post-intervention), and 12-month survey (See **Appendix 8** for Survey and **Appendix 13** for baseline cover letter and **Appendix 14** for follow-up cover letter). The survey will be available online. It will also be available on paper if the participant prefers or administered via telephone if there are accessibility issues (**Appendix 8**).

EW-D Survey Data: Participants in the EW-D arm (group 1) will complete an additional survey designed to assist the Wellness Coach with tailoring the intervention sessions (**Appendix 9**). Participants will complete it at baseline (prior to intervention), 3-month (mid-intervention), 7-month (post-intervention), and 12-month survey. Participants will complete the survey on paper and the de-identified survey responses will be entered and stored on the Sound Generations network (the data will allow Sound Generations to accrue supporting data for their intervention). It may also be administered via telephone if there are accessibility issues.

Missing data/survey: For both the self-report survey and the EW-D survey, after research staff receive the completed survey, they will review it and contact the participant if there is any missing data using the missing data script (**Appendix 15**). Research staff will attempt to contact the participant up to 3 times for missing data. This script will also be used to remind participants about unreturned surveys and consent forms.

Withdrawal from study:

Participants who are withdrawn by study staff: We will withdraw enrolled participants who are unreachable after multiple attempts. Participants who have been non-responsive (attempted to contact them (via phone or email) no fewer than 3 times and no more than 6 times over a 4-week period) to attempts by research staff and the wellness coach to schedule visits or follow up on survey mailings will be withdrawn from this study (**Appendix 12**). During our last few contact attempts, we will let participants know that we'll conclude their participation if we do not hear back within 2 weeks. They will also be notified that if they would like to re-join the study, then they can contact us at their convenience.

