***NOTE:** For both electronic and paper consent methods, research staff will not be witnessing the participant sign the consent form and **we are requesting a waiver of verifying the identity (i.e. via video call) of the participant signing the consent form**. We believe this waiver is justified because there are no legal/financial risks to UW, safety risks to the participant, or scientific risks to the study if someone other than the participant who is not an intended signatory signs the consent form. If a participant informs study staff that an unintended signatory signed the consent form, study staff will shred that participant's consent form and request a video call with the participant to witness the participant sign the paper or electronic consent form.

After Completing Consent: Once the participant completes informed consent, they will be sent their Baseline survey and GPS/Travel Diary (if applicable). After completing the baseline survey, the participant will be randomized to a study arm. Because individuals will be consented prior to randomization into a study arm, the consent form has detailed information about procedures involved in all three study arms.

Consent Process for Pilot Study:

After an individual is recruited for the pilot study, research staff will send them the study information statement (**Appendix E**) in a packet along with the intervention study materials they will be asked to review. The individual will be asked to read the information sheet and contact the research team with any questions. Prior to starting the pilot procedures, study staff will ask the participant if they have any questions about the research and/or the procedures.

c. **Comprehension.** Describe how you will ensure or test the subjects' understanding of the information during the consent process.

We will answer any questions that participants may have about the study. When responses appear inappropriate or inconsistent (eg, individual's responses contradict their previous responses) during screening, staff (in consultation with the PI) may decide to exclude them from the study. To ensure the participants understand the purpose of the research, we included 3 questions from the UBACC Decisional Capacity Questions in the Recruitment Script (Appendices 3 and A).

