Statistical Analysis Plan for University of Washington School of Medicine,

Department of Rehabilitation Medicine study:

Efficacy and mechanism of a community wellness promotion program for middle-aged adults living
with long-term physical disability

PI: [name], PhD

NCT 03653390

UW IRB STUDY00007984

Initial IRB Approval: April 11, 2018

Document Last Updated: October 26, 2023

Statistical Analysis Plan

Design overview:

- 3-arm, randomized controlled trial
 - Arm 1: Enhance Wellness for Disability (8 sessions)
 - Arm 2: Health education (8 sessions of the CDC's "Keys to Healthy Aging")
 - Arm 3: Treatment as usual (TAU)
 - 6-month intervention period across 3 groups
 - 12-month follow-up across 3 groups

Assessment timeline:

- Patient reported outcomes collected at baseline (pre-randomization), and at 3, 6 and 12 months post-randomization
- GPS outcomes collected at baseline (pre-randomization) and at 12-month follow-up

Primary outcome variable:

1. Change in ability to participate in social roles and activities
 - Measured via the PROMIS Ability to Participate in Social Roles and Activities 8-item short form
 - Patient reported outcome
 - Results recorded as a t score

Secondary outcome variables (patient reported):

1. Change in satisfaction with social role participation
 - Measured via the PROMIS Satisfaction with Social Roles and Activities 8-item short form
 - Results recorded as a t score

2. Change in disease management self-efficacy
 - Measured via the University of Washington Self-Efficacy Scale, 6 item short form
 - Results recorded as a t score
3. Change in interference due to pain
 - Measured via the PROMIS-29 Profile, v. 2.1 pain interference subscale (4 items)
 - Results recorded as a t score
4. Change in interference due to fatigue
 - Measured via the PROMIS-29 Profile, v. 2.1 fatigue subscale (4 items)
 - Results recorded as a t score
5. Change in psychological resilience
 - Measured via the Connor-Davidson Resilience Scale, 10-item short form
 - Scores range from 0-40

Secondary outcome variables (GPS and travel log based):

1. Change in number of trips outside the home
 - Mean average per day
2. Change in radius of gyration
 - Results recorded in meters
3. Change in number of trips outside the home containing “social” elements
 - Based on integration of GPS and travel log report
4. Change in time of trips spent in activities outside of the home containing “social” elements
 - Results recorded in minutes

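### Is the baseline GPS week really collected before randomization, as the SAP says?

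*Protocol*

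**What the plan says.** The SAP's assessment timeline reads "GPS outcomes collected at baseline (pre-randomization) and at 12-month follow-up". The label covers all three arms.

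The protocol times randomization in two places, both by the survey: section 5.1 (Study Arm Randomization), "After completing the baseline survey, individuals will be randomized into one of the three study arms", and section 8.2b (After Completing Consent), "After completing the baseline survey, the participant will be randomized to a study arm". Just before the second of these, section 8.2b says that once consent is complete "they will be sent their Baseline survey and GPS/Travel Diary (if applicable".

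The survey is short ("completion time is about 45 minutes", section 5.1, Group 1) and "The survey will be available online", with paper or telephone as alternatives. The GPS part is slower: "Participants will be mailed a cover instruction letter, along with the portable GPS data logger", and "a subset of participants (N=100 per arm; 300 total) will be invited to a one week GPS/diary study component" at baseline and at 12 months. Staff may ask for a repeat week if the GPS data are unusable. For Groups 1 and 2, section 5.1 places both the survey and the baseline GPS week before the first session.

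**The concern.** The two baselines run on different clocks, and the protocol ties randomization to the faster one. Read literally, a participant could finish the survey online, be randomized, and wear the logger for the baseline week afterwards. The SAP label would then be untrue for that participant.

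Sessions could not contaminate such a baseline, because the GPS week precedes the first session in both active arms and treatment as usual has no sessions. Anticipation could. Someone who knows the arm during the baseline week might change how often they go out. That shift would enter the change score that the SAP compares by ANOVA, in a direction that cannot be predicted. The exposed outcomes are the four GPS and travel-log secondaries.

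**Working it through.** **1. Inputs and the plan's own figures.** Section 4.4 confirms the 7-day wear period: $10 × 7 days × 2 weeks = $140, and $25 × 4 surveys + $140 = $240, both as stated. The GPS subset is 100 × 3 = 300, also as stated. The documents give no mail time. I assume 0 to 7 days, with wear starting on the day of receipt (offset 0) or the next day (offset 1).

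**2. How far apart the two baselines can be.** Take the survey as finished on the day the materials are sent (day 0). Then last GPS day = mail days + offset + 6.

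| Mail days (assumed) | Last GPS day, offset 0 | Last GPS day, offset 1 |
|---|---|---|
| 0 | 6 | 7 |
| 1 | 7 | 8 |
| 3 | 9 | 10 |
| 7 | 13 | 14 |

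The gap is at least 7 days in every case except same-day delivery with same-day wear. A repeat week lengthens it; a participant who answers the survey later shortens it. This is the gap that staff may have to wait out. It does not show that anyone was randomized inside it.

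**3. Whether the sentences conflict.** The protocol requires randomization after the survey. The SAP requires randomization after the GPS week. Randomizing at the later of the two completions meets both. With 3 days of mail and a day-0 survey, that is after the last GPS day, day 9 or 10. A conflict would need a sentence saying that randomization follows the survey at once, or that the GPS week may come after allocation. No visible sentence says either.

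**4. How much the protocol's silence proves.** Section 5.1 is abbreviated elsewhere too. Its overview says that study-group procedures start once consent is received and the baseline survey is complete, without naming the GPS week. Yet the Group 1 and Group 2 procedures require that week before sessions. The overview therefore leaves out a GPS precondition that does exist, and the same omission in the randomization sentence carries little weight.

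**5. What the dispatch sentence implies.** Section 8.2b sends the GPS diary with the survey, where applicable, before allocation. Membership of the GPS subset must then be settled before the arm is known. The figure of 100 per arm does not contradict this: with equal arms (assumed), 600 / 3 = 200 per arm, and the GPS half (300 / 600) of each is 100.

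**6. Consequence.** Let *s* be the one-arm shift in outings caused by knowing the arm, and *p* the average share of the baseline week that falls after the participant learns it. The bias in that arm's mean change is about *s* × *p* in size. Under the order in step 3, *p* = 0 and the bias is 0. Otherwise *p* depends on survey turnaround, mail time and the date the arm is disclosed, and *s* on behaviour; judging the effect on the test also needs the GPS means and standard deviations. The documents give none of these, so a bias or error rate would reflect only the values chosen, and I give none.

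**The case for a change.** The strongest case for acting is that sending materials before allocation is not the same as completing them before allocation, and that the rule placing GPS before sessions does not fix its order relative to randomization. Treatment as usual does not have even that rule. Anticipation is also plausible here: participants must have a goal in mind in case they are assigned to EW-D, the consent form describes all three arms, and EW-D goals may include more socializing, which is close to what the GPS outcomes measure. Nothing visible says when participants learn their arm.

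All of this is accurate, and it shows that the visible protocol text would permit early randomization if the SAP were ignored. It does not show that the plan as a whole permits it, because the SAP states the order for every arm. Section 5.1 also refers the reader to Figure 1 and to a randomization script (Appendix 23). The figure is not reproduced and the script is not supplied, so their content cannot be counted as missing.

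One narrow point stands. If a first week proves unusable and the participant has already been randomized, the repeat week falls after allocation and the SAP label does not fit it. The documents do not say how often this happens. Changing the general order would not remove it unless randomization were held for every repeat week.

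**Conclusion.** No change follows. The SAP states that the GPS baseline precedes randomization, the protocol states that the survey does, and both hold if staff wait for the later of the two. The protocol simply does not repeat the GPS condition in its randomization sentences, and a team using both documents fills that gap sensibly.

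If the stated order is followed, the effect on any result is zero. If it were not, the exposure would be limited to four secondary outcomes in an optional subset of 300 of 600, through anticipation only. The primary outcome is survey-based, and both documents put its baseline before randomization. The SAP was last updated in October 2023 and describes its methods in the past tense, so enrollment is probably over and rewording the protocol would alter no data.

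This rests on two assumptions: that staff applied the SAP's order, and that the unseen figure and script do not contradict it. Nothing in the visible text speaks against either.

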Although the expectation is a total of 8 calls over a six-month period (2 in each of the first 2 months, one per month thereafter), participants may request up to 2 additional calls if they require support with a particular challenge (up to 10). The number of follow up visits will vary depending on the participant's desires and his or her program goals. These visits will involve a review of the health action plan and discussing progress toward reaching goals. To monitor for fidelity to the intervention, a random selection of sessions will be audio-recorded and reviewed (with participant consent) by the study PI, designated study staff, and/or an EnhanceWellness Master Trainer at Sound Generations.

Participant's Valued Outcomes	Action Plan Goals (established with coach)	Action Steps for Participant	Wellness Coach Roles
"I want to eat better, lose some weight and become more physically active"	1. Improve nutrition 2. Increase exercise to 30min, 3x/wk 3. Lose 5% of body weight in 6 months	1. Ask MD for referral to nutritionist 2. Call insurance company regarding referral to Physical Therapy for exercise training 3. Attend an adapted exercise program at the YMCA 4. Purchase bathroom scale	1. Work on development of Action Plan 2. Provide letter to participant's physician stating involvement in program and asking for any additional target areas 3. Provide participant with community resources for increased physical activity 4. Provide participant with support in making step by step plans to achieve complex goals (for example, what to ask insurance company re: physical therapy) 5. Help participant identify and overcome barriers to goals 6. Help participant identify social support resources to achieve goals 7. Provide feedback to participant on progress
"I want to get better control of my pain."	1. Decrease pain interference 10%	1. Attend a local pain self-management support group 2. Ask MD for pain and medication information 3. Attend adapted yoga class	

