GROUP 2: Wellness Education To control for expectancy effects and Wellness Coach contact time, we will include an educational time control condition based on eight 45 minute sessions of telephone or Zoom-based wellness education, also delivered over 6 months. These sessions will also be administered by a UW study Wellness Coach (called the social worker for this study arm). The session timing is designed to match the EW-D group (2 sessions in the first month, one per month thereafter). For this control condition, participants will discuss material presented in the CDC's "10 Keys to Healthy Aging" program, developed by the University of Pittsburgh

(see manual: **Appendix 22**). These sessions provide participants will health information in 10 key areas, 8 of which have been selected for this trial. These are: (1) blood pressure management, (2) maintaining social contact, (3) cancer screening, (4) regulation of blood glucose, (5) decreasing LDL cholesterol, (6) physical activity, (7) bone, joint and muscle health and (8) immunizations. In addition to the 8 sessions with the interventionist, participants will be provided with informational material by mail or email.

Procedures: Prior to starting their wellness education sessions, participants will complete the baseline study survey (Appendix 8) and GPS baseline (if randomized to the GPS group). Then, we will connect the participant with the social worker to schedule their first session (all sessions will be conducted over the telephone or Zoom HIPAA compliant video call). During each session, the social worker will review the health topic selected for that session (Appendix 22). The participant will receive the handout included for that topic in the manual, but they will not be asked to complete the homework listed in the manual. If the participant does not have any issues with the topic selected for that session (eg, they have normal blood pressure), the social worker will review information on how to maintain their blood pressure. To monitor for fidelity to the intervention, a random selection of telephone sessions and Zoom HIPAA compliant video calls will be audio-recorded and reviewed (with participant consent) by the study PI and/or designated study staff.

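### The education arm is meant to control for coach contact time, but planned minutes are not matched: 360 against about 480 in EW-D at the expected 8 sessions

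*Protocol*

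**What the plan says.** Protocol section 5.1, Group 2, gives the education arm its purpose and its session length in one sentence: "To control for expectancy effects and Wellness Coach contact time, we will include an educational time control condition based on eight 45 minute sessions". The deliverer is of the same type as in EW-D: "These sessions will also be administered by a UW study Wellness Coach (called the social worker for this study arm"). Both arms use telephone or Zoom over 6 months. On the calendar, the section states: "The session timing is designed to match the EW-D group (2 sessions in the first month, one per month thereafter").

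Section 5.1, Group 1, describes EW-D. On length, "each session is expected to last about 1 hour". On number, "the expectation is a total of 8 calls over a six-month period (2 in each of the first 2 months, one per month thereafter"). Beyond that, "participants may request up to 2 additional calls if they require support with a particular challenge (up to 10"), and "The number of follow up visits will vary depending on the participant's desires and his or her program goals". The paragraph on physician screening calls also puts the EW-D intervention at 8 to 10 calls and says that the physician calls come on top of these.

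The SAP, under Design overview, lists "Arm 1: Enhance Wellness for Disability (8 sessions") and gives 8 sessions for the education arm as well. Under Statistical Approach, pairwise differences are examined with Tukey's HSD only after a significant omnibus ANOVA. Contact time is not mentioned there.

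**The concern.** Sections 1.3 and 1.5 of the protocol call the education arm an attention control. TAU participants have no contact with a study social worker (section 5.1, Group 3), so EW-D versus education is the only contrast that can separate what the program contains from the attention that comes with it. The protocol names coach contact time as one of the things this arm controls, yet the two arms are given different session lengths and different room for extra calls.

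The primary outcome is patient reported, and no blinding is described (section 10.6 is answered as not applicable). If the contrast is tested and EW-D does better, a reader who relies on the stated purpose of the education arm would take contact time as held equal and credit the difference to content. The planned minutes do not support that step.

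**Working it through.** The documents give no total of contact minutes for either arm, so the only stated figure to reproduce is the session count.

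**Session counts from the stated schedules, over 6 months**
- EW-D: 2 in each of the first 2 months, then one per month: 2 + 2 + 4 × 1 = 8. This reproduces the stated 8.
- Education: 2 in the first month, then one per month: 2 + 5 × 1 = 7. This does not reproduce the stated 8, and the pattern is not the EW-D pattern that it is said to match.

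**Planned coach minutes = sessions × minutes per session**

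Inputs: 8 sessions in each arm (protocol 5.1 and SAP Design overview); 45 minutes for education (5.1, Group 2); about 60 minutes for EW-D (5.1, Group 1). The physician screening calls are not coach time and are left out.
- Education: 8 × 45 = 360.
- EW-D: 8 × 60 = 480. Difference 480 − 360 = 120 minutes; ratio 480/360 = 1.33.

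**Sensitivity to the approximate hour (assumed values)**
- 55 minutes: 8 × 55 = 440; 440/360 = 1.22.
- 50 minutes: 8 × 50 = 400; 400/360 = 1.11.
- At 8 sessions each, the arms are equal only if EW-D sessions average 360/8 = 45 minutes.

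**Upper end of the planned EW-D range**
- 10 calls: 10 × 60 = 600, against 360. Difference 240 minutes; ratio 1.67. No extra sessions are described for education.

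**Education schedule taken literally**
- 7 × 45 = 315, against 480. Difference 165 minutes; ratio 1.52. The stated number is 8, so this shows only what the inconsistency could mean. It is not the main figure.

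**The case against.** The strongest reply is that the protocol states an aim and never claims equal minutes. The 45-minute length stands in the same sentence as that aim, the only match it explicitly says was designed concerns session timing, and both lengths are open to any reader. The two lengths describe different arms, so they do not contradict each other. All of this is right, and it limits the point: nothing is concealed, and the arms do share deliverer type, mode, period and an expected 8 sessions. But the sentence names contact time as a thing controlled and calls the arm a time control. The plan does not deliver that property, and no passage says so or gives a reason.

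A second reply is that the size is soft. The 33% depends on reading about one hour as 60 minutes. This also stands, and the range at 8 calls is 11% to 33%. The direction does not change within that range.

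A third reply is that EW-D contact varies with the participant, so delivered minutes might have come out equal. The documents leave delivered contact open. The planned range for EW-D, however, runs upward from 8 to 10 calls, not downward.

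A reader might go further and infer that the arms received unequal contact, that the EW-D versus education result is biased by some known amount, or that the education arm fails as a control. The documents support none of these. They give no delivered sessions or minutes and no estimate of how contact affects the outcome, and several features of contact are shared.

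**Conclusion.** The statement about controlling contact time is wrong as written. At the expected 8 sessions per arm, EW-D is planned at about 120 more coach minutes than education, about 33% more (11% to 22% if sessions are assumed to last 50 to 55 minutes). With the 10 calls that the protocol allows, the excess could reach about 240 minutes. These are planning figures. The EW-D versus education contrast is partly, not fully, controlled for contact.

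The consequence is for attribution. The size of any effect on the patient-reported outcome cannot be worked out from the documents, and no error rate, sample size or EW-D versus TAU result is affected. The count of 7 against 8 in the education schedule is a separate inconsistency, and the conclusion on minutes does not depend on it.

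**What to change.** 1. Reconcile the session text in protocol section 5.1, Groups 1 and 2, on number, timing and length. Which schedule or length applies is for the study team to state.
2. Restate the purpose sentence for the education arm: the two arms share deliverer type, mode, 6-month period and an expected 8 sessions, but they are not matched on planned contact minutes or on optional extra calls.
3. State, in the SAP or where the results are interpreted, that a difference between EW-D and education cannot be attributed to content alone with contact time held equal.
4. Report delivered sessions by arm beside that contrast, and minutes if they were recorded.

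The cost is a few sentences and one small table. The SAP describes its tests in the past tense, so this concerns wording and reporting, not delivery. The table depends on data that may not exist: the documents describe no log of session minutes, and section 10.1 says that recording was to be paused during COVID-19 and that some sessions may not be recorded. Without such data, only the wording changes apply. The downside is a more modest claim for the attention-control contrast.
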